# 8.7 Assessment of Compliance

Compliance with scheduled use of Investigational Product will be determined from the Subject's diary. Subjects will be instructed to bring their daily diary and used and unused study drug containers at all scheduled visits or Early Discontinuation Visit to allow for tablet count and compliance checks. Subjects will also be asked to record in a daily diary the date and time at which they took the study drug. In addition, Subjects will be instructed to document all AEs on the diary.

If the subject does not return the Diary, Subject-reported dosing compliance will be recorded in the source notes and will be used to derive compliance between those visits.

For scheduled visits greater than 4 weeks apart, subjects will be called (at w8, w32, w40) and asked about compliance with study drug.

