6.8 Study Drug Exposure and Compliance

Duration of exposure will be defined as follows:

[Date of Last Dose] – [Date of First Dose] + 1

For subjects initially randomized to AS012, Date of Last Dose is collected at the End of Study eCRF and Date of First Dose is collected at the Study Drug Administration eCRF at Visit 2. In case Date of Last Dose is not collected at the End of Study eCRF (e.g. the subject is lost to follow-up), the date of last dose will be assumed to be equal to the date of the last visit in the study.

Duration of exposure will also be defined separately for Part I of the study and Part II of the study.

For Part I, Date of Last Dose is the date preceding the date of study drug administration at Visit 7/Week 24, provided the subject is administered drug at Visit 7; otherwise, it is the Date

of Last Dose as collected at the End of Study eCRF. The Date of First dose is collected at the Study Drug Administration eCRF at Visit 2.

For Part II the Date of Last Dose is collected at the End of Study eCRF and Date of First Dose is collected at the Study Drug Administration eCRF at Visit 7/Week 24.

Compliance will be calculated in terms of total number of tablets taken separately for Part I, Part II and both parts overall. Compliance will be defined in two ways:

- 1. Based on the diary data as (9*[Number of planned treatment days] [Total number of missed tablets]) / (9*[Number of planned treatment days]) *100%
- 2. Based on the drug accountability data as ([Total number of drug bottles dispensed]*105 [Total number of tablets returned])/ (9*[Number of planned treatment days]) *100%. This is based on the assumption that each dispensed bottle contained 105 tablets.

Number of planned treatment days will be defined as follows:

- For Part I
 - For subjects that completed Part I, i.e. attended Week 24 visit: [Date of Week
 24 Visit] [Date of the first dose of the study drug]
 - For subjects that discontinued in Part I: [Date of discontinuation] [Date of the first dose of the study drug] + 1
- For Part II
 - For subjects that completed Part II, i.e. attended Week 52 visit: [Date of Week 52 Visit] [Date of Week 24 Visit] + 1
 - For subjects that discontinued in Part II: [Date of discontinuation] [Date of Week 24 Visit] + 1
- For overall compliance (for subject initially randomized to AS012)
 - For subjects that completed Part II, i.e. attended Week 52 visit: [Date of Week 52 Visit] [Date of the first dose of the study drug] + 1

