 - For subjects that discontinued in Part I or Part II: [Date of discontinuation] –
 [Date of the first dose of the study drug] + 1

Total number of missed tablets will be calculated form the diary data by summing up the values "Total Number of Missed Tablets Per Diary (At Morning)", "Total Number of Missed Tablets Per Diary (At Afternoon)" and "Total Number of Missed Tablets Per Diary (At Evening)" transcribed at the "Study Drug Accountability" eCRF across applicable visits, i.e:

- For Part I: visits up to and including Week 24 Visit, including any unscheduled visits occurring before Week 24 Visit date
- For Part II: visits after Week 24 Visit, including any unscheduled visits occurring after Week 24 Visit date
- For overall compliance (for subject initially randomized to AS012); all visits

If the subject did not return the diary at least once and therefore the number of missed tablets is not known, the compliance will not be calculated.

Total number of dispensed bottles and total number of returned tablets will be calculated from the "Study Drug Accountability" eCRF by summing up the appropriate fields across the applicable visits.

For subjects initially randomized to placebo overall compliance will be calculated separately for Placebo treatment in Part I and for AS012 treatment in Part II.

Subject will be defined as non-compliant if the subject missed more than 14 continuous days of treatments. Information on missing more than 14 continuous days of treatments will be derived from the subject diaries by the sites and entered into eCRF.

Duration of exposure and compliance (both definitions) will be summarized descriptively by treatment group for the Safety population, separately for Part I and for the entire study. Number and percentage of non-compliant subjects will also be provided. In the summary for the entire study subjects initially randomized to Placebo in Part I and re-randomized to AS012 in Part II of the study will be summarized under both treatments they received.

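### SAP 6.8 does not calculate diary compliance when a diary is not returned, contradicting the subject-report rule in protocol 8.7 and discarding diary data that were returned

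*SAP*

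**What the plan says.** **Protocol 8.7.** The diary is the main source: "Compliance with scheduled use of Investigational Product will be determined from the Subject's diary". If it is not returned, "Subject-reported dosing compliance will be recorded in the source notes and will be used to derive compliance between those visits". For visits more than four weeks apart there is a further contact: "subjects will be called (at w8, w32, w40) and asked about compliance with study drug".

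**SAP 6.8.** "Compliance will be defined in two ways":

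- The diary measure takes planned tablets (nine a day) minus missed tablets, divided by planned tablets. Missed tablets are summed over all applicable visits of Part I, of Part II, or of both.
- The second measure is "Based on the drug accountability data as ([Total number of drug bottles dispensed]*105" less the tablets returned, divided by nine times the planned treatment days. It uses no diary.

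The missing-diary rule is that where someone "did not return the diary at least once and therefore the number of missed tablets is not known, the compliance will not be calculated". On reporting: "Duration of exposure and compliance (both definitions) will be summarized descriptively by treatment group for the Safety population". One such summary covers Part I and another covers the whole study. Overall compliance across both parts is defined only for subjects first randomized to AS012. Placebo-start subjects are computed separately for Part I and Part II.

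The SAP's non-compliance flag also relies on diaries: "Information on missing more than 14 continuous days of treatments will be derived from the subject diaries by the sites and entered into eCRF".

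**The concern.** Both documents foresee the same event, a diary that does not come back, and prescribe different handling. The protocol has sites collect the subject's own account so that the interval can be filled. The SAP (Amendment 1, 27 July 2022) is later than the protocol (20 May 2022), yet its visible text neither uses that information nor explains why it is set aside.

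Because missed tablets are summed over visits, one unknown term makes the whole sum unknown. The SAP resolves this by giving no value, so intervals with good diary data are lost along with the one that is missing.

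At stake is a descriptive summary. In a dose-ranging trial with nine tablets a day for 52 weeks, compliance by arm helps a reader interpret the dose comparison. That summary should cover as many subjects as the collected data allow.

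**Working it through.** The documents give no compliance rate and no diary return rate, so there is no plan figure to reproduce. The check is a comparison of the two rules, followed by a calculation of scale under stated assumptions.

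**1. The two rules side by side**

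| | Protocol 8.7 | SAP 6.8 |
|---|---|---|
| Interval without a diary | Filled with subject-reported dosing | Missed tablets treated as unknown |
| Intervals with a returned diary | Kept | Lost, because no value is calculated for the period |
| Result for the subject | A compliance value | No diary-based value |

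The SAP sentence does not say which of its two measures it switches off. Its stated reason, that missed tablets are unknown, applies only to the diary formula.

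**2. Number of diaries needed.** Protocol sections 7.4, 7.7, 7.9, 7.11 and 7.12 have the treatment diary collected at Visits 4, 7, 9, 11 and 12. That is 2 in Part I, 3 in Part II and 5 overall.

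**3. Share of subjects without a diary value.** Assume each diary is returned independently with probability r and that any one missing diary triggers the rule. The share is 1 − r^k for k diaries.

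| r (assumed) | Part I, k = 2 | Part II, k = 3 | Overall, k = 5 (AS012-start only) |
|---|---|---|---|
| 98% | 1 − 0.98² = 4.0% | 5.9% | 9.6% |
| 95% | 1 − 0.95² = 9.8% | 14.3% | 22.6% |
| 90% | 1 − 0.90² = 19.0% | 27.1% | 41.0% |

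With about 64 subjects per arm, the Part I column is about 2.5, 6.2 and 12.2 subjects per arm. These shares apply to subjects who owe every diary; early discontinuers owe fewer.

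The whole-study summary needs five diaries from an AS012-start subject, but two and then three, separately, from a placebo-start subject. With identical return behaviour (r = 95%), it would therefore lose 23% of values in one group, and 10% (Part I) and 14% (Part II) in the other.

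**4. The other reading.** If *at least once* means that no diary was ever returned, the Part I share is (1 − r)²: 0.04%, 0.25% or 1% for the same three rates.

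**5. Possible bias.** Let f be the share excluded and d the mean compliance of included minus excluded subjects. The reported mean then differs from the full mean by f × d. At an assumed f = 20%:

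- d = 0 gives 0 points.
- d = 10, 20 or 30 points gives +2, +4 or +6 points.
- d = −10 points gives −2 points.

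The documents give neither f nor d.

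**6. The tablet count as a backstop.** Unreturned tablets count as taken. In Part I the nominal planned days are 169 − 1 = 168, or 9 × 168 = 1,512 tablets. One unreturned 105-tablet bottle adds 105 / 1,512 = 6.9 percentage points.

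**The case against.** The strongest reply is that little depends on this. A subject with a missing diary can still have an accountability-based value, and both measures are summarized. Compliance is descriptive, and in the visible text it does not enter the ITT population, the imputation or the ANCOVA. This stands, and it limits the severity. The backstop is imperfect, however: a subject who brings back neither diary nor bottles has no diary value and an inflated tablet count.

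A second reply is that subject recall may itself overstate adherence, so the protocol's rule is not clearly less biased than leaving the value missing. That is fair. It is a reason to flag substituted intervals. It is not a reason to discard intervals with a returned diary, or to depart from the protocol without saying so.

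A third reply is that the independence assumption overstates the loss. If non-return clusters in a few subjects, fewer are excluded: should the same 5% of subjects fail to return every diary, the loss is 5%, against 10% (Part I) or 23% (overall) under independence. This also stands; the percentages show scale and are not forecasts.

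A reader might infer more: that the rule removes the least adherent subjects, biases reported compliance upward, overstates exposure by dose, and could make a flat dose response look like lack of drug effect. The documents do not support this. Neither links diary return to adherence. The tablet-count measure does not depend on diaries. Duration of exposure is computed from first and last dose dates. The step to a misread dose response is speculation.

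**Conclusion.** The SAP is wrong as written on this point, because its rule for an unreturned diary contradicts protocol 8.7. The severity is low.

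On the natural reading, diary-based compliance will be missing for the period concerned for any subject with one missing diary, even where the other diaries were returned. The size depends on a return rate that the documents do not give: 4% to 19% of subjects for Part I, and 10% to 41% of AS012-start subjects overall, at assumed independent returns of 98% to 90% per diary. If the sentence means that no diary was ever returned, the Part I loss is at most 1% at those rates.

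Upward bias in the diary measure is possible if non-return goes with poor adherence, but it is not established. The flag for more than 14 days missed may share the gap, since the SAP states no fallback for it. Any link to analysis populations or deviation rules that are redacted cannot be judged.

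**What to change.** In SAP 6.8, replace the sentence with the protocol 8.7 rule: for an interval without a returned diary, use the subject-reported missed doses, and keep the diary data from every other interval. This also removes the ambiguity over *at least once*. If the departure from the protocol was intended, the SAP should say so and give the reason.

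The protocol places the subject's report in the source notes, so confirm that the figure is entered on the Study Drug Accountability eCRF. Flag substituted intervals, and report by arm the number of subjects with substituted intervals and the number with intervals still missing. Keep the tablet-count measure separate rather than blending it into the diary measure. State how the 14-day flag is handled when a diary is missing.

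The cost is SAP wording and perhaps one eCRF field. The downside is small: self-report is less precise than a diary and may itself overstate adherence, which is why the substituted intervals should be visible.

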6.9 Efficacy Analyses

6.9.1 Analysis of the primary endpoint

6.9.1.1 Imputation of the primary endpoint

VASI total score will be calculated as explained in Appendix IV to the protocol. Missing Week 24 assessments of VASI will be imputed using multiple imputations methods. For each subject in the ITT population with missing endpoint 50 imputations will be performed using Fully Conditional Specifications (FCS) predictive mean matching imputation model with the factors of the primary analysis model (i.e., treatment, stability of disease [stable vs. non-stable at screening], and baseline VASI score as a covariate,) and VASI score at Week 12. Each imputed dataset will be analyzed as described in the next section. The results will be combined using Rubin's rule. See Section 11.2.1 for detailed description of the imputation procedure and SAS sample code.

[figure not shown]
6.9.1.2 Primary analysis of the primary endpoint

The primary endpoint will be summarized descriptively by treatment group.

Note that approximately 5 sites will be designated to perform VASI, and VES by two independent assessors to test reliability and validity of the instruments (see Section 6.9.2.7). Only the assessment by the first assessor will be used for the primary endpoint.

The primary endpoint will be analyzed with an Analysis of Covariance (ANCOVA) model to compare change from baseline in VASI score results between treatment arms at Week 24. The ANCOVA model will include fixed effects for treatment, stability of disease (stable vs. non-stable at screening), and baseline VASI score as a covariate. Point estimates and 95% confidence intervals as well as p-values for the hypothesis of no difference will be obtained for the difference between each active dose versus placebo.

Type I error will be preserved in the primary efficacy analysis by use of a closed test step-down approach. Beginning with the highest total daily dose, pairwise comparisons to placebo will be made in the following sequence:

Number and percentage of subjects achieving these endpoints will be presented by treatment group along with 95% confidence interval for percentages based on binomial proportion.

Maintenance of these endpoint will be assessed by presenting the number and percentage of subjects maintaining these endpoints at Week 64 among those who achieved them at Week 52.

6.9.2.3 Categorical endpoints

[figure not shown]
Categorical endpoints include . Number and percentage of subjects with each category of response will be presented by treatment group and visit.

[figure not shown]
6.9.2.4 Time to re-pigmentation

Times to re-pigmentation of 10%, 25%, 75%, 90% and 100% are defined as the time from the first dose of the study drug to the first assessment where VASI 10, VASI 25, VASI 75, VASI 90 and VASI 100 correspondingly are achieved. The time will be measured in weeks. For subjects who never achieved the corresponding VASI reduction, the time will be censored at the last VASI assessment.

For subjects who are initially randomized to placebo time to re-pigmentation will be defined separately for the Placebo treatment during Part I of the study and AS012 treatment during Part II of the study. For Placebo treatment the time to re-pigmentation will start with the first placebo dose and will be censored at the last VASI assessment while on placebo. For AS012 treatment the time will start with the first AS012 dose and will be censored at the last assessment after the switch to AS012.

Quartiles of time to re-pigmentation over the 52 weeks of treatment with their 95% confidence intervals will be calculated by treatment group.

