### Clinical Evaluations will be performed at:

```
Visit 1: Screening Visit (Week ≥ -4 / Day -28 to -1);
Visit 2: Baseline Visit (Week 1 / Day 1);
Visit 3: Interim Visit (Week 4 / Day 29 ± 3 Days);
Visit 4: Interim Visit (Week 12 / Day 85 ± 3 Days);
Visit 5: Interim Visit (Week 16 / Day 113 ± 3 Days);
Visit 6: Interim Visit (Week 20 / Day 141 ± 3 Days);
Visit 7: Interim Visit (Week 24 / Day 169 ± 3 Days);
Visit 8: Interim Visit (Week 28 / Day 197 ± 3 Days);
Visit 9: Interim Visit (Week 36 / Day 253 ± 3 Days);
Visit 10: Interim Visit (Week 44 / Day 309 ± 3 Days);
Visit 11: Interim Visit (Week 48 / Day 337 ± 3 Days);
Visit 12: End of Treatment Visit (Week 52 / Day 365 ± 3 Days);
Visit 13: Follow-up Visit (Week 64 / Day 449 ± 3 Days);
```

Subjects will be admitted into the study after informed consent has been obtained. An Unscheduled Visit is allowed at any time, for any reason, if in the Principal Investigator's opinion it is warranted. If a Subject is discontinued from the study during an Unscheduled Visit, the Unscheduled Visit will be referred to as an Early Discontinuation Visit. For all the subjects who discontinue the study prior to Visit 7 all efforts should be made to conduct a visit at, or close to week 24 to collect focused area assessments. Regardless of the reason, subjects discontinued from IP prior to the end of study will be required to complete the End of Study (EoS) assessment within 2 weeks after the last dose.

[figure not shown]
Randomization and re-randomization will be stratified by stability of disease (stable vs. non-stable)

The assigned Investigational Product will be administered orally three tablets three times a day, in the morning, in the afternoon, and in the evening according to a randomization scheme. Subjects will be required to use diaries to document the date of study treatments, any missed treatments and the occurrence of all adverse events.

[figure not shown]
The duration of each Subject's participation in the study will be approximately 64 weeks (449 days).

If the Principal Investigator determines that the Subject's condition has worsened to the degree that it is unsafe for the Subject to continue in the study (e.g. an increase in VASI score from baseline by  $\geq 25\%$ ), the Subject may be discontinued from the study as a treatment failure and the Subject may be treated using the standard care.

May 20, 2022 Protocol: **AS012-20-01** Page 20 of 88

May 20, 2022 Protocol: **AS012-20-01** Page 21 of 88

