The assigned IP will be administered orally three tablets three times a day, in the morning, in the afternoon, and in the evening according to a randomization scheme. Subjects will be required to use diaries to document the date of study treatments, any missed treatments, and the occurrence of all adverse events (AEs).

The duration of each Subject's participation in the study will be approximately 64 weeks (449 days).

If the Principal Investigator determines that the Subject's condition has worsened to the degree that it is unsafe for the Subject to continue in the study (e.g., an increase in VASI score from baseline by $\geq 25\%$), the Subject may be discontinued from the study as a treatment failure and treated using the standard care.

A detailed Schedule of Procedures is provided in Appendix 11.1.

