3.2 Sample Size

The study will randomize approximately 320 subjects into 5 treatment arms (n=approximately 64 subjects per arm) in a 1:1:1:1:1 ratio. The sample size assumes a drop-out rate of about 20%, with 52 evaluable subjects per treatment arm at the time of analysis. The study is powered at 85%, and assumes a two-sample Z-test with equal variances, two-sided alpha (α) of 0.05, a Baseline VASI mean of 15.7 and standard deviation of 8.9 and an improvement at Week 24 of 35% (Δ 5.50) for AS012 versus an improvement for placebo of 10% (Δ 1.56), for a mean treatment difference of 3.94. Since the correlation between Baseline and Week 24 VASI scores is expected to be >0.5, the standard deviation of the difference is conservatively estimated at 70% of the Baseline SD, or 6.4. The sample size takes into account an interim assessment of futility and efficacy, using an O'Brien-Fleming error spending function to determine the boundaries, once the placebo, dose reach 75% completion of the Week 24 VASI assessment. Randomization will be stratified by stability of disease (stable vs. non-stable) With a total of six possible stratification levels, 52 evaluable subjects per treatment arm ensures at least 8 subjects per stratification level.

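### Time to re-pigmentation (SAP 6.9.2.4) censors subjects withdrawn because VASI worsened, so the censoring is informative and estimated response is biased upward by an amount the documents do not fix

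*SAP*

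**What the plan says.** **Event and output (SAP 6.9.2.4).** The times to re-pigmentation "are defined as the time from the first dose of the study drug to the first assessment where VASI 10, VASI 25, VASI 75", 90 or 100 is reached. The planned output is quartiles: "Quartiles of time to re-pigmentation over the 52 weeks of treatment with their 95% confidence intervals will be calculated by treatment group". No estimator is named, but quartiles with confidence intervals from censored times imply Kaplan-Meier.

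**Censoring (same section).** There is one rule for all non-achievers: "For subjects who never achieved the corresponding VASI reduction, the time will be censored at the last VASI assessment". For subjects first randomized to placebo, the Part I time is censored at the last VASI on placebo and a separate AS012 clock starts after the switch. The visible text of this section has no separate handling for subjects withdrawn for worsening and no sensitivity analysis.

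**Withdrawal for worsening.** When the investigator judges that worsening makes it unsafe to continue, SAP 3.1 says "the Subject may be discontinued from the study as a treatment failure and treated using the standard care". Protocol 3 has the same provision: "the Subject may be discontinued from the study as a treatment failure and the Subject may be treated using the standard care". Both give a VASI increase of at least 25% from baseline as an example.

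**Drop-out (SAP 3.2).** "The sample size assumes a drop-out rate of about 20%, with 52 evaluable subjects per treatment arm at the time of analysis". The share due to worsening is not given.

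**The concern.** Kaplan-Meier assumes that a censored subject has the same future chance of the event as those still under observation. A subject withdrawn because VASI went the wrong way does not. That subject has left assigned treatment, and the reason for leaving is read off the scale that defines response. Censoring nevertheless credits the subject with the later response rate of those who remained, who are doing better by selection.

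The curves, and the quartiles taken from them, then describe response in a population from which failures have been removed. In a dose-ranging trial, readers will look at time to response arm by arm, even if no test is attached.

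**Working it through.** The documents state no event rate, quartile or power for this endpoint, so there is no planned figure to reproduce. The check covers direction first and then size.

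**Inputs from the documents:** about 64 subjects per arm, total drop-out about 20%, baseline VASI mean 15.7, SD of change 6.4, mean improvement at Week 24 of 5.50 (AS012) and 1.56 (placebo), all from SAP 3.2. **Not in the documents:** the share *f* of an arm withdrawn for worsening, the response rate, and the timing of withdrawals. VASI at Weeks 12 and 24 is visible in Protocol 7.4 and 7.7. VASI at Weeks 36 and 52 is assumed, because those lists are blacked out.

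**1. Direction.** At a visit with *d* responders and *n* subjects at risk, the present rule uses *d/n*. Keeping *w* earlier failures at risk as non-responders gives *d/(n+w)*, which is never larger. Estimated cumulative response under the present rule is therefore at least as high at every visit, and no quartile can be later.

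**2. How many subjects might worsen by 25%.** The cut-off is 0.25 × 15.7 = 3.925 points upward. With normal changes:
- AS012: P(Z > (3.925 + 5.50)/6.4) = P(Z > 1.47) = 0.070
- Placebo: P(Z > (3.925 + 1.56)/6.4) = P(Z > 0.86) = 0.196

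These are shares reaching the example threshold at Week 24, not shares withdrawn.

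**3. Closed-form upper bound.** Suppose a share *f* never respond and are all censored before any event. Kaplan-Meier then estimates F(t), while response in the whole arm is (1−f)F(t). With exponential times, the time to quantile *p* lengthens by ln(1 − p/(1−f)) / ln(1 − p).

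| f | Response when Kaplan-Meier shows 50% | First quartile, ratio | Median, ratio |
|---|---|---|---|
| 2% | 0.98 × 50 = 49.0% | 1.024 | 1.030 |
| 5% | 0.95 × 50 = 47.5% | 1.062 | 1.078 |
| 10% | 0.90 × 50 = 45.0% | 1.131 | 1.170 |
| 20% | 0.80 × 50 = 40.0% | 1.302 | 1.415 |

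The last row assigns all the assumed drop-out to worsening.

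**4. Visit-grid simulation.** 64 per arm, VASI at Weeks 12, 24, 36 and 52, failures' last VASI at Week 0, 12, 24 or 36 with equal probability, 4,000 runs. With 60% true response by Week 52 among non-failures:

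| f | Week 52, present rule | Week 52, failures kept at risk | Gap (points) | Arms with an earlier median |
|---|---|---|---|---|
| 5% | 59.3% | 57.1% | 2.2 | 6% |
| 10% | 58.1% | 53.9% | 4.2 | 19% |
| 20% | 56.4% | 48.0% | 8.4 | 48% |

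With true response from 35% to 80%, the gap ran from 1.2 points (34.5 − 33.3, f = 5%) to 11.9 points (76.0 − 64.1, f = 20%). No run gave a later first quartile or median. At f = 5% the median moved in at most 7% of arms.

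**5. Correlated-VASI simulation, AS012 arm.** This uses the SAP 3.2 inputs. It assumes visit correlation 0.5 or 0.75, mean improvement growing a further 50% from Week 24 to Week 52, and SD growing with the square root of time to a cap. A stated share of subjects at +25% or worse is withdrawn.

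| Share of those subjects withdrawn | Week 52 gap, VASI 25 | Week 52 gap, VASI 75 |
|---|---|---|
| 15–25% | about 1.5–3 points | about 1–2 points |
| 50–100% | about 5–11 points | about 3–7 points |

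On the planned output, the VASI 25 first quartile (Week 12) and median (Week 24) and the VASI 75 first quartile (Week 36) did not change in any scenario. The VASI 25 third quartile and the VASI 75 median moved in some. At visit correlation 0.5, for example, VASI 75 response at Week 52 was 0.51–0.53 under the present rule and 0.46–0.47 otherwise, which changes the median from Week 52 to not reached.

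**The case against.** The strongest reply is that little of this shows in what the SAP reports. Section 6.9.2.4 plans quartiles only, with no cumulative response at Week 52, no hazard ratio and no between-arm test. With few VASI visits, quartiles move in whole-visit steps and mostly stay put. **This stands**, and it limits the point to a bias that can only go one way.

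Second, a 25% rise is not a withdrawal trigger. It is an example of worsening judged unsafe, after which the subject may be discontinued. Protocol 5.10 asks for re-evaluation in that case. Protocol 4.6 lists unsafe worsening among the reasons for removal, but that too rests on the investigator's judgement. **This stands:** withdrawing half or all such subjects is an assumption. Its upper end needs roughly 15–20% of an AS012 arm withdrawn for worsening alone, close to the whole assumed drop-out of about 20%.

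Third, the model in step 5 is rough. The SAP itself calls the SD of 6.4 conservative, so the worsening tail may be inflated, and normal changes put some subjects below a VASI of 0. **This stands** against the size, not the direction.

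Fourth, Protocol 7.15 seeks a visit near Week 24 for early leavers and an end-of-study assessment within 2 weeks of the last dose. A later VASI can delay censoring. **This stands in part:** such a VASI may be taken on standard care, and the visible SAP text does not say whether it counts for the AS012 arms.

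Finally, SAP 6.1.2 draws no inference from p-values outside the primary endpoint. **This stands** and sets the priority, but descriptive summaries should still estimate what they appear to estimate.

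**Conclusion.** The point holds as a bias of known direction and unknown size. The rule makes censoring depend on the outcome score. Estimated response on assigned treatment is therefore biased upward, and quartiles can be too early but never too late.

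Under the assumed models, the Week 52 overstatement is roughly 1 to 3 points if few worsening subjects are withdrawn. It rises to about 11 if all are; the visit-grid model reaches 11.9 points when all the assumed drop-out is worsening. The third quartile for VASI 25 and the median for VASI 75 are most exposed. The Week 24 primary analysis is not touched.

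Three stronger readings are tempting and are not supported:
- *That the reported quartiles will be too early throughout.* Most did not move in the simulations.
- *That 7% of AS012 and 20% of placebo subjects will be withdrawn for worsening.* Those are modelled shares at an example threshold, under a rule that leaves withdrawal to judgement.
- *That the comparison between doses is biased.* The distortion would differ if failures differ by arm, so this is possible. But no formal comparison is visible, only one AS012 effect was modelled, and no contrast over a common window was computed. More failures on placebo would inflate placebo more over a common period, which would work against the drug.

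Parts of SAP 6.9.2 are withheld from the public text, so a rule elsewhere cannot be excluded; 6.9.2.4 itself reads as complete.

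**What to change.** Amend SAP 6.9.2.4 as follows:

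- Treat discontinuation for treatment failure (worsening or lack of efficacy) before response as a competing event. Estimate the cumulative incidence of each re-pigmentation level (Aalen-Johansen) and take the quartiles from that curve.
- Alternatively, keep these subjects at risk as non-responders to the end of the period: Week 24 for placebo in Part I, and Week 52 for AS012, including the Part II AS012 period of subjects switched from placebo. Without other drop-out the two give the same estimate.
- Censor only other drop-out and administrative end of follow-up.
- State whether a VASI taken after withdrawal, or on standard care, can count as a response or set the censoring time.
- Name the estimator, and keep the present rule as a supportive analysis.

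The cost is a few sentences and a small change to the survival code. Discontinuation reasons are already recorded (Protocol 4.6, SAP 6.2), so no new data or visits are needed and no rule of clinical management changes. The downside is that response curves will look slightly less favourable.
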